## 5.2 Treatment Regimen

The interventions were be performed post-operatively in the PACU. See the following sections for more detail as to how the study interventions will be carried out.

## 5.3 Method for Assigning Subjects to Study Interventions

After patients are enrolled and consented to the study, they will be randomized to receive either an autofill or backfill void trial post-hysterectomy in the PACU. The randomization process will be completed by one study personnel prior to the initiation of the study using a random number generator. The random assignment of backfill void trial or autofill void trial will be placed in envelopes prior to enrollment of the first patient. The prepared envelopes will be used in sequential order. After hysterectomy is completed and prior to the participant emerging from anesthesia, the envelope will be opened informing the surgical team which group the participant randomizes to. The study intervention will then be carried out as below.

## 5.4 Preparation and Administration of Study Intervention

Participants who randomize to the backfill void trial will remain with a Foley catheter in place or will have the Foley catheter replaced, in the case that a cystoscopy is performed. The participant will emerge from anesthesia under routine monitoring and will be transferred to the PACU when meeting appropriate criteria per anesthesia discretion. Once the participants are awake and meeting criteria for discharge, the patients in the backfill group will undergo a void trial by a PACU nurse or by a doctor if the nurse is unavailable. About 300 mL of fluid will be instilled into the bladder and the Foley will then be removed. The participant will be given up to 1 hour to urinate and the amount urinated will be recorded using a commode specimen collection

measurer. The PVR will be measured using a bladder scanner. If the PVR is greater than 100 mL or if the patient is unable to void within the hour, the void trial will be considered "failed" and a Foley catheter will be replaced. Patients who randomize to the autofill void trial will be given a 500 cc bolus of crystalloid by the anesthesia team prior to leaving the operating room. These participants will be allowed to urinate at any time within the first 3 hours after surgery. The amount urinated will be recorded using a commode specimen collection measurer. The PVR will be measured using a bladder scanner. If the PVR is greater than 100 mL, the void trial will be considered "failed" and a Foley catheter will be replaced. We anticipate that most of these patients will void spontaneously within 2 hours of arrival to the PACU. At two hours postoperatively, any patient who cannot void or does not have the urge to void will have a bladder scan. If the patient has more than 300 cc in the bladder, she will be allowed 1 more hour to void. If she cannot, a Foley catheter will be placed and she will be considered to have failed the void trial. If the patient has less than 300 cc in the bladder, another 500 cc of crystalloid bolus will be given and we will await void for another hour. At 3 hours post-operatively, these patients will undergo another bladder scan. Those with greater than 300 cc of urine in the bladder will receive a Foley catheter. Those with less than 300 cc of urine in the bladder will have a backfill void trial by placing the remaining amount of fluid into the bladder for a total volume of 300 cc. The rest of the void trial will be completed as per normal backfill void trial protocol. The participants who have a replaced Foley catheter will receive education regarding usage of a leg bag and will be discharged home to return to the office the following business day where a repeat void trial will be performed using the backfill method as previously outlined. If participants are unable to be discharged home, they will be admitted overnight in the hospital with documented rationale. A backfill void trial will then be performed the following day. If participants fail the 2nd void trial, a Foley catheter will be replaced and will remain in place for 1 week, at which time a backfill void trial will be repeated once again in the office. If this void trial is failed as well, participants will be educated about and asked to perform self-catheterization at home and will follow up with Urogynecology.

# 5.5 Subject Compliance Monitoring

Since the study interventions will both be completed by a study personnel or a trained nurse, compliance is not applicable to this study.

#### 5.6 Prior and Concomitant Therapy

Concomitant antibiotic therapy or immunosuppressive therapy will be recorded but will not preclude the patients from being a part of the study.

#### 5.7 Packaging

Foley catheters and leg bags are both packaged in a sterile fashion. Additionally, sterile water will be used to fill the bladder in the backfill void trials.

#### 5.8 Blinding of Study Agent

The participants will not be blinded to the study interventions due to the nature of the void trials and their timing in relation to the participants' surgeries. Additionally, the study personnel will not be blinded to the study interventions and outcomes because they will be responsible for carrying them out and setting up follow up appointments as needed for the participants.

# 5.9 Receiving, Storage, Dispensing and Return

## 5.9.1 Receipt of Drug (Device or Treatment) Supplies

Foley catheters are used for every laparoscopic hysterectomy performed at Cleveland Clinic Florida. These are charged to the participant as part of her surgery. Void trials will not require any extra supplies outside of the scope of the surgery and all supplies are available to the nurses and study personnel in the operating rooms and PACU.

## 5.9.2 Storage

All necessary supplies are available in the operating rooms and in the PACU.

## 5.9.3 Dispensing of Study Drug (or Device)

The supplies are self-serve and can be found in the clean supply rooms of both operating rooms.

## 5.9.4 Return or Destruction of Study Drug (or Device)

This section is not applicable as Foley catheters are thrown away in biohazard trash cans as per routine.

#### **6.0 STUDY PROCEDURES**

# 6.1 Pre-registration and Screening

All patients scheduled for TLH will be offered enrollment in the study per the above inclusion and exclusion criteria. Eligibility will be confirmed at this time by a member of the research team through patient interview and review of the available electronic health record. All enrolled participants will have a PVR checked and recorded in the clinic using the bladder scanner that is available to us or straight catheterization. The enrolled participants will also be asked to complete the Patient Perception of Bladder Condition (PPBC) and the Incontinence Impact Questionnaire-Short Form (IIQ-7) and the completed forms will be collected by the research team (see attached "Preoperative participant questionnaire"). 9,10

## 6.2 Surgery

On the surgical day, all enrolled participants will undergo standard registration and preoperative preparation by the staff pre-operative nurse, including placement of intravenous access line and administration of standard preoperative medications. The participant will be taken to the operating room. Induction, intubation, and anesthesia will be administered according to standard practice by a dedicated group of anesthesia providers. Prior to surgical incision, preoperative prophylactic antibiotics will be administered. The participant will be positioned in the dorsal lithotomy position with the lower extremities in the Allen stirrups bilaterally and the bilateral upper extremities in a tucked position. Surgical sterile preparation and draping will be performed per usual technique. Foley catheter will be placed prior to the start of the surgical procedure. The hysterectomy will then proceed in the usual manner. After the specimen is removed from the pelvis and the vaginal cuff is closed, a cystoscopy may be performed at the discretion of each surgeon. At this time, the randomization envelope will be opened. Participants who randomize to the backfill void trial will remain with a Foley catheter in place or will have the Foley catheter replaced, in the case that a cystoscopy is performed. Those in the autofill group will have a 500

cc bolus of crystalloid prior to leaving the operating room. All skin incisions will be closed in a subcuticular fashion and sealed with skin adhesive. The participant will emerge from anesthesia under routine monitoring and will be transferred to the PACU when meeting appropriate criteria per anesthesia discretion.

## 6.3 Post-op Day 0 in PACU

Once the patient is awake and meeting requirements for discharge, the void trials can take place. Participants who randomize to the backfill void trial will remain with a Foley catheter in place or will have the Foley catheter replaced, in the case that a cystoscopy is performed. The participant will emerge from anesthesia under routine monitoring and will be transferred to the PACU when meeting appropriate criteria per anesthesia discretion. Once the participants are awake and meeting criteria for discharge, the patients in the backfill group will undergo a void trial by a PACU nurse or by a doctor if the nurse is unavailable. About 300 mL of fluid will be instilled into the bladder and the Foley will then be removed. The participant will be given up to 1 hour to urinate and the amount urinated will be recorded using a commode specimen collection measurer. The PVR will be measured using a bladder scanner. If the PVR is greater than 100 mL or if the patient is unable to void within the hour, the void trial will be considered "failed" and a Foley catheter will be replaced. Patients who randomize to the autofill void trial will be given a 500 cc bolus of crystalloid by the anesthesia team prior to leaving the operating room. These participants will be allowed to urinate at any time within the first 3 hours after surgery. The amount urinated will be recorded using a commode specimen collection measurer. The PVR will be measured using a bladder scanner. If the PVR is greater than 100 mL, the void trial will be considered "failed" and a Foley catheter will be replaced. We anticipate that most of these patients will void spontaneously within 2 hours of arrival to the PACU. At two hours postoperatively, any patient who cannot void or does not have the urge to void will have a bladder scan. If the patient has more than 300 cc in the bladder, she will be allowed 1 more hour to void. If she cannot, a Foley catheter will be placed and she will be considered to have failed the void trial. If the patient has less than 300 cc in the bladder, another 500 cc of crystalloid bolus will be given and we will await void for another hour. At 3 hours post-operatively, these patients will undergo another bladder scan. Those with greater than 300 cc of urine in the bladder will receive a Foley catheter. Those with less than 300 cc of urine in the bladder will have a backfill void trial by placing the remaining amount of fluid into the bladder for a total volume of 300 cc. The rest of the void trial will be completed as per normal backfill void trial protocol. The participants who have a replaced Foley catheter will receive education regarding usage of a leg bag and will be discharged home to return to the office the following business day where a repeat void trial will be performed using the backfill method as previously outlined. If participants are unable to be discharged home, they will be admitted overnight in the hospital with documented rationale. A backfill void trial will then be performed the following day. If participants fail the 2nd void trial, a Foley catheter will be replaced and will remain in place for 1 week, at which time a backfill void trial will be repeated once again in the office. If this void trial is failed as well, participants will be educated about and asked to perform self-catheterization at home and will follow up with Urogynecology.

# 6.4 Post-op Day 1 Visit (applicable only if 1st void trial fails)

Participants who fail the post-hysterectomy void trial (their 1st void trial) will be scheduled for a nurse visit on POD1, where a repeat void trial will be performed using the backfill method as

previously outlined. If the participant was admitted to the hospital, a backfill void trial will then be performed the following day in the hospital. If participants fail the 2nd void trial, a Foley catheter will be replaced and will remain in place for 1 week.

# 6.5 Post-op Week 1 Visit (applicable only if 2nd void trial fails)

Participants who fail the POD1 void trial (their 2nd void trial) will be scheduled for a nurse visit after one week, at which time a backfill void trial will be repeated once again in the office. If this void trial is failed as well, participants will be educated about and asked to perform self-catheterization at home and will follow up with Urogynecology for further management.

## 6.6 Post-op Week 2 Visit

At the post-operative visit 10-14 days after the surgery, the participants will be evaluated and examined in the office. They will be asked to complete a questionnaire which includes the IIQ-7, the PPBC, and a void trial satisfaction question (see attached "post-operative participant questionnaire"). Participants will also be asked if they obtained a Foley catheter outside of the hospital at any urgent care centers, other doctors' offices, or emergency rooms. Additionally, participants will be asked if they have any urinary problems including dysuria, hematuria, frequency, hesitancy, urgency, or incomplete emptying. If any urinary complaints exist, participants will be asked to provide a urine sample for testing by urinalysis and urine culture. Participants will be treated per physician preference. After treatment, participation in the study will be considered completed.

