## 2.2 Secondary Objectives

The following variables will also be compared between participants undergoing backfill void trial and autofill void trial:

- Time to discharge: time from arrival to post-anesthesia care unit (PACU) to time of discharge
- Incidence of urinary retention after discharge from hospital
- Incidence of UTI in the first 2 weeks after surgery
- Participants' short term quality of life during the first 2 weeks after surgery
- Participants' satisfaction with the void trials

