## 3.3 Secondary Study Endpoints

The following study endpoints will also be compared between participants undergoing backfill void trial and autofill void trial:

- The time to discharge will be measured for each participant. This will be determined by calculating the time between arrival to the PACU and the time of discharge using documentation from Epic and from the case report forms (CRFs).
- After discharge, participants will be monitored for any encounters for urinary retention (in our hospital system) and will be asked at their 10-14 day post-operative visit if they had a Foley catheter placed outside the hospital. Additionally, any participant who fails their 2nd void trial will be noted. The incidence of urinary retention post-discharge will be determined using this data.
- Any participant diagnosed with a culture-proven UTI will be noted.
- The IIQ-7 will be used to determine if there are any changes to the participants' short term quality of life before and after surgery.
- The PPBC will be used to determine if there are any changes to the participants' perception of bladder function before and after surgery.

- Participant satisfaction level with the method of void trial will be collected at the 10-14 day post-operative visit and compared between the two methods of void trial.

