# **6.8 Laboratory Procedures**

No samples will be sent to the laboratory within the study.

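### UTI in the first two weeks is at risk of under-ascertainment, because no defined search covers infections treated before, outside or after the single day 10-14 visit

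*Combined protocol and SAP*

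**What the plan says.** All references are to the combined protocol and SAP.

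- **Objective and definition.** Section 2.2 lists "Incidence of UTI in the first 2 weeks after surgery" among the outcomes compared between arms. Section 3.3 says: "Any participant diagnosed with a culture-proven UTI will be noted". It names no source of cases and no method of finding them.
- **How a culture comes about.** At the day 10-14 visit, "participants will be asked if they have any urinary problems including dysuria, hematuria, frequency, hesitancy, urgency, or incomplete emptying" (Section 6.6; Section 3.1 says the same). Then: "If any urinary complaints exist, participants will be asked to provide a urine sample for testing by urinalysis and urine culture". The question is in the present tense. Participation ends after this visit and any treatment that follows.
- **Care received elsewhere.** At the same visit women are "asked if they obtained a Foley catheter outside of the hospital". Section 3.3 adds monitoring of encounters in the site's own system, for urinary retention. Neither provision mentions UTI.
- **Laboratory.** The calendar in Section 6.7 has no urine-test row, and Section 6.8 states: "No samples will be sent to the laboratory within the study".
- **Unequal contact.** The POD1 and week-1 visits (6.4, 6.5) apply only after a failed void trial. Section 5.8 says that neither participants nor study personnel are blinded.

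**The concern.** The outcome is incidence over two weeks, but the specified means of finding it looks at one moment. A woman treated for a UTI at an outside clinic in the first week, and well by the visit, has no current complaint and so triggers no culture. A woman seen on day 10 who develops a UTI on day 12 falls within the two-week window but after her last study contact. The authors foresaw outside care, since they ask about catheters placed elsewhere, yet UTI has no matching safeguard.

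Section 6.8 adds a contradiction: read literally, it leaves no room for the culture on which the definition depends.

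At stake are the accuracy of a stated secondary outcome and, if detection depended on how often a woman is seen, the fairness of its comparison between arms. The primary endpoint is not affected.

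**Working it through.** **Figures in the plan.** The plan gives no expected rate, power or sample size for UTI, so there is no UTI figure to reproduce. Its 38 per group (76, or 84 with 10% added: 76 × 1.10 = 83.6) is for void trial failure at 28.3% versus 4.9% (Section 7.1). The standard two-proportion formula gives 39 per group, either one-sided with continuity correction or two-sided without, and 31 one-sided without correction. The UTI point does not depend on this. I use only the arm size of 38 and the two failure rates.

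**1. Window.** Days left uncovered = 14 − visit day. A day-10 visit leaves 4 (4/14 = 29%); a day-14 visit leaves 0. This is a share of days, not of infections.

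**2. Ascertainment set side by side.**

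| | Retention after discharge | UTI |
|---|---|---|
| In-system encounters monitored | Yes (3.3) | Not specified |
| Outside care asked about | Yes, catheter placement (3.1, 3.3, 6.6) | No specific question |
| Test trigger | Second void trial for those who fail the first | Complaint present at day 10-14 |

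**3. Size of under-counting.** The only UTI rates in the documents are 4%, 6% and 18%, by catheter duration, from a cited trial in laparoscopic-assisted vaginal hysterectomy (Section 1.3). They are illustrative here. Expected true cases per arm of 38 are 38 × 0.04 = 1.5, 38 × 0.06 = 2.3 and 38 × 0.18 = 6.8. One missed case changes an arm's rate by 1/38 = 2.6 percentage points.

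The detected share is unknown, so I show a range, the same in both arms. For true rates p₁ and p₂ and detected share s, the observed rates are sp₁ and sp₂. Power at n = 38, two-sided 0.05, is

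Φ{[|d|√n − 1.96√(2p̄(1−p̄))] / √(p₁(1−p₁) + p₂(1−p₂))},

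with the observed rates as p₁ and p₂, d their difference and p̄ their mean. For 6% versus 18%:

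| Share detected (assumed) | Expected recorded cases | Power |
|---|---|---|
| 100% | 2.3 vs 6.8 | 36% |
| 80% | 1.8 vs 5.5 | 29% |
| 60% | 1.4 vs 4.1 | 23% |
| 40% | 0.9 vs 2.7 | 16% |

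For 4% versus 6%, power is about 6% even with full detection. With counts this small the approximation is rough.

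**4. Could detection differ by arm?** At the planning failure rates, a POD1 visit is expected for 38 × 0.283 = 10.8 backfill and 38 × 0.049 = 1.9 autofill women (11.9 and 2.1 at 42 per arm). Let s₀ be the detected share without an extra visit, s₁ the share with one, and f the failure rate. Overall detection in an arm is s₀(1 − f) + s₁f. Take equal true risk in both arms:

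| s₀ / s₁ (assumed) | Backfill | Autofill | Spurious ratio |
|---|---|---|---|
| equal | s₀ | s₀ | 1.00 |
| 80% / 100% | 0.857 | 0.810 | 1.06 |
| 50% / 90% | 0.613 | 0.520 | 1.18 |
| 50% / 100% | 0.642 | 0.525 | 1.22 |

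Excluding the equal case, at a true risk of 6% to 18% the spurious difference runs from 0.06 × (0.857 − 0.810) = 0.3 points to 0.18 × (0.642 − 0.525) = 2.1 points. Multiplied by 38, that is 0.1 to 0.8 of a woman per arm.

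**The case against.** The best defence is that the plan has other routes to a UTI record. The statement in 3.3 is not limited to the day 10-14 visit. Section 8.2 requires specific questioning about adverse events at each contact, and a UTI fits the definition in 8.1. Medical history is taken from everyone at week 2 (6.7), concomitant antibiotics are recorded (5.6), and Epic is the main source record (9.2). The CRF and questionnaires are listed as attachments but are not among the documents, and may ask more. A reader might infer that UTI can be found only through complaints at one visit and that outside infections are never asked about; these routes rule out so strong a claim. They still do not amount to a defined UTI search. None requires an outside culture to be retrieved, Epic is the site's own record, and antibiotic recording has no stated period or indication while all women without a contraindication receive prophylaxis.

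A reader might also infer that 6.8 bars cultures and makes the endpoint unobtainable. It can equally be read as excluding research samples, with symptom-driven cultures being clinical care. It does not say so, and the conflict with 3.1 and 6.6 stands, but as a matter of wording.

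Finally, a reader might infer that UTI will be detected unequally between arms. The documents do not show this. The culture trigger is the same in both arms. The extra visits are for repeat void trials and specify no UTI check. Most would be on POD1, too early for an infection arising later in the first week, and the plan gives no rate for the second failure that leads to a week-1 visit.

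It is also fair to say that better ascertainment will not make this comparison well powered. That limits the importance of the point but is no reason to leave inexpensive gaps open.

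**Conclusion.** Two-week UTI incidence is at risk of under-ascertainment. Followed as written, the specified procedure can miss a UTI treated elsewhere and resolved, or one arising after a visit held before day 14. The size of the loss cannot be derived from the documents. With 1.5 to 6.8 expected cases per arm of 38, borrowed from a different procedure, even one or two missed cases would matter to the reported rates.

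Differential detection is possible, through extra visits after failure, voiding complaints that trigger a culture, and the absence of blinding. It is not demonstrated. The extra-visit route comes to less than one woman per arm under every assumption tried; the other two routes cannot be sized from the documents.

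This is an inexpensive improvement to a secondary outcome and has no bearing on the primary result.

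**What to change.** 1. At the day 10-14 visit, ask every participant whether a UTI has been diagnosed or treated since surgery, where, and whether a culture was sent. Request the result if one was.
2. Check Epic for positive urine cultures through day 14 for every participant, in the same way in both arms. Name this check and the question above in Section 3.3 as the sources for the endpoint.
3. Reconcile Section 6.8 with 3.1 and 6.6, so that it allows the urinalysis and culture sent for urinary complaints.

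Keep the culture-proven definition; culturing women without symptoms is not needed.

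The cost is one CRF question and one record check per participant, some effort to obtain outside results, and one corrected sentence. No visit is added. One limit remains: a UTI treated elsewhere without a culture will still not count.
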